##### **a. Expedited IND Safety Reports:**

##### **7 Day calendar Telephone or Fax Report:**

The Sponsor-Investigator is required to notify the FDA of any event that is serious, unlisted/unexpected and assessed by the investigator to be possibly related to the use of study drug(s). An unexpected adverse event is one that is not already described in the Investigator Brochure. Such reports are to be telephoned or faxed to the FDA as soon as possible but no later than 7 calendar days of first learning of the event. Each telephone call or fax transmission (see fax number below) should be directed to the appropriate FDA fax number.

Sites are required to submit MedWatch3500A reports no later than 5 business days after being informed of an event.

#### **12.0 REMOVAL OF PATIENTS FROM PROTOCOL THERAPY**

Extraordinary medical circumstances or withdrawal of consent by the patient: If, at any time, the constraints of this protocol are detrimental to the patient's health, and/or the patient no longer wishes to continue protocol therapy, the patient shall be withdrawn from protocol therapy. Patients will also be withdrawn from study for the following reasons:

**Disease Progression: Any patient with disease progression should be removed from study. Details and tumor measurements should be documented on flow sheets. See section 7 regarding defining progression on study.**

1. Patient is unable to tolerate the toxicity resulting from the study treatment, even with optimal supportive care, in the opinion of the Treating Physician. Adverse event(s) that, in the judgment of the investigator, may cause severe or permanent harm or which rule out continuation of study drug.
2. The physician feels it is in the best interest of the patient to stop the treatment.

3. Inter current illness that would, in the judgment of the Investigator, affect assessment of clinical status to a significant degree or require discontinuation of study treatment
4. Non protocol chemotherapy or immunotherapy is administered during the study
5. Noncompliance with protocol or treatment—major violation
6. Suspected Pregnancy
7. Patient is lost to follow-up
8. Patient refuses to continue treatment (patient will continue to be followed for disease-free survival and overall survival)
9. Death

In this event notify:

### **13.0 FOLLOW-UP**

All Subjects that discontinue treatment early for any reason as well as patients who complete therapy will be followed for five years. At treatment discontinuation, subjects will undergo adverse event evaluation and again approximately 30 days post the last dose of study drug. In addition off study evaluations will be done when treatment is discontinued -Section 6.0.

### **14.0 REGULATORY CONSIDERATIONS**

This research study is sponsored by the Principal Investigator, [name], in collaboration with Brown University Oncology Research Group (BrUOG), which will serve as the central coordinating office for the study.

#### **14.1 Protection of Human Subjects**

The Investigator must ensure that patients or their legally acceptable representatives are clearly and fully informed about the purpose, potential risks and other critical issues regarding clinical trials in which they volunteer to participate. Preparation of the consent form is the responsibility of the Investigator and must include all elements required by CFR 21 Part 50.25 and the local IRB.

#### **14.2 Compliance with the Protocol and Protocol Revisions:**

The study must be conducted as described in this approved protocol.

All revisions to the protocol must be provided to Brown University Oncology Research Group. The Investigator should not implement any deviation or change to the protocol without prior review and documented approval/favorable opinion from the IRB/IEC of an Amendment, except where necessary to eliminate an immediate hazard(s) to study patients.

Documentation of approval signed by the chairperson or designee of the IRB(s)/IEC(s) must be sent to Brown University Oncology Research Group. If the revision is an Administrative Letter, Investigators must inform their IRB(s)/IEC(s).

The Investigator must ensure that patients or their legally acceptable representatives are clearly and fully informed about the purpose, potential risks and other critical issues regarding clinical trials in which they volunteer to participate. Preparation of the consent form is the responsibility

of the Investigator and must include all elements required by CFR 21 Part 50.25 and the local IRB.

After the study has been fully explained, written informed consent will be obtained from either the patient or his/her guardian or legal representative prior to study participation. The method of obtaining and documenting the informed consent and the contents of the consent will comply with ICH-GCP and all applicable regulatory requirement(s).

#### **14.3 Protocol amendments or changes in study conduct:**

- Any change or addition (excluding administrative) to this protocol requires a written protocol amendment that must be reviewed and approved by Brown University Oncology Research Group, and the investigator before implementation. Amendments significantly affecting the safety of subjects, the scope of the investigation or the scientific quality of the study require additional approval by the IRB at each study center. A copy of the written approval of the IRB must be provided to Brown University Oncology Research Group

Examples of amendments requiring such approval

- Increases in drug dose or duration of exposure of subjects
- Significant changes in the study design (e.g. addition or deletion of a control group)
- Increases in the number of invasive procedures
- Addition or deletions of a test procedure required for monitoring of safety.

These requirements for approval should in no way prevent any immediate action from being taken by the investigator or by Brown University Oncology Research Group in the interests of preserving the safety of all patients included in the trial. If an immediate change to the protocol is felt to be necessary by the investigator and is implemented for safety reasons Brown University Oncology Research Group must be notified and the IRB at the center must be informed immediately. Amendments affecting only administrative aspects of the study do not require formal protocol amendments or IRB approval but the IRB must be kept informed of such administrative changes.

### **15.0 DATA MONITORING / QUALITY ASSURANCE/ RECORD RETENTION**

**15.1 Good Clinical Practice:** The study will be conducted in accordance with the International Conference on Harmonisation (ICH) for Good Clinical Practice (GCP) and in the US Code of Federal Regulations. The investigator will be thoroughly familiar with the appropriate use of the drug as described in the protocol. Essential clinical documents will be maintained to demonstrate the validity of the study and the integrity of the data collected. Master files should be established at the beginning of the study, maintained for the duration of the study and retained according to the appropriate regulations.

**15.2 Patient Confidentiality:** In order to maintain patient privacy, all data capture records, drug accountability records, study reports and communications will identify the patient by initials and the assigned patient number. The investigator will grant monitor(s) and auditor(s) from BrUOG or its designees and regulatory authority (ies) access to the patient's original medical records for verification of data gathered on the data capture records and to audit the data collection process. The patient's confidentiality will be maintained and will not be made publicly available to the extent permitted by the applicable laws and regulations.

**15.3 Protocol Compliance:** The investigator will conduct the study in compliance with the protocol given approval/favorable opinion by the IRB/IEC and the appropriate regulatory

FDA exemption 6/30/15, 6/30/15, 8/17/15 (for LOCR initial), Amendment #1 10/5/15 v 2 HS approval, Amendment # 2 11/9/15, Amendment #3 3/4/16, Amendment # 4 4/7/16, Amendment # 5 6/1/16 V2, Amendment # 6 7/7/16, Amendment # 7 11/16/16, Amendment # 8 2/22/17, Amendment #9 5/22/17

authority(ies). Changes to the protocol will require approval from BrUOG and written IRB/IEC approval/favorable opinion prior to implementation, except when the modification is needed to eliminate an immediate hazard(s) to patients. The IRB/IEC may provide, if applicable regulatory authority(ies) permit, expedited review and approval/favorable opinion for minor change(s) in ongoing studies that have the approval /favorable opinion of the IRB/IEC. The investigator will submit all protocol modifications to BrUOG and the regulatory authority(ies) in accordance with the governing regulations.

Any departures from the protocol must be fully documented in the source documents.

**15.4 On-site Audits:** Regulatory authorities, the IEC/IRB and/or BrUOG clinical quality assurance group may request access to all source documents, data capture records, and other study documentation for on-site audit or inspection. Direct access to these documents must be guaranteed by the investigator, who must provide support at all times for these activities.

**15.5 Drug Accountability:** Accountability for the drug at all study sites is the responsibility of the principal investigator. The investigator will ensure that the drug is used only in accordance with this protocol. Drug accountability records indicating the drug's delivery date to the site (if applicable), inventory at the site (if applicable), use by each patient will be maintained by the clinical site. Accountability records will include dates, and patient numbers.

**15.6 Premature Closure of the Study:** This study may be prematurely terminated, if in the opinion of the investigator or BrUOG, there is sufficient reasonable cause. Written notification documenting the reason for study termination will be provided to the investigator by the terminating party.

Circumstances that may warrant termination include, but are not limited to:

- Determination of unexpected, significant, or unacceptable risk to patients
- Failure to enter patients at an acceptable rate
- Insufficient adherence to protocol requirements
- Insufficient complete and/or evaluable data
- Plans to modify, suspend or discontinue the development of the drug

### **15.7 Record Retention:**

The investigator will maintain all study records according to ICH-GCP and applicable regulatory requirement(s).

The Brown University Oncology Research Group, as coordinator of this study, is responsible for ensuring proper conduct of the study with regard to protocol adherence and the validity of the data recorded on the case report forms. The Principal Investigator ([name].) and Brown University Oncology Research Group Director of Operations ([name]) will monitor this study. The case report forms will be monitored for accuracy, completeness, adherence to the protocol and regulatory compliance.

U.S. FDA regulations (21CFR312.62[c]) require all records and documents pertaining to the conduct of this study and the distribution of investigational drug, including CRFs, consents forms, laboratory test results and medication inventory records, must be retained by the Principal Investigator for 2 years after marketing application approval. If no application is filed, these records must be kept 2 years after the investigation is discontinued and the FDA and the applicable local health authorities are notified.

## **16.0 DATA SAFETY AND MONITORING BOARDS**

All trials initiated by the Brown University Oncology Research Group (BrUOG) are subject to

oversight by the Data Safety Monitoring Board (DSMB). This board meets two times per year with any additional meetings scheduled when needed. The responsibilities are as follows:

- Familiarize themselves with the research protocol (s)
- The DSMB reviews trial performance information such as accrual information.
- Review interim analyses of outcome data and cumulative toxicity data summaries to determine whether the trial should continue as originally designed, should be changed, or should be terminated based on these data.
- The DSMB also determines whether and to whom outcome results should be released prior to the reporting of study results.
- All adverse events are reviewed by the committee, with assurances that these have been in fact sent for review to all pertinent IRBs.
- Review of reports of related studies to determine whether the monitored study needs to be changed or terminated.
- Review major proposed modifications to the study prior to their implementation (e.g., termination, dropping an arm based on toxicity results or other reported trial outcomes, increasing target sample size).
- Following each DSMB meeting, provide the study leadership with written information concerning findings for the trial as a whole related to cumulative toxicities observed and any relevant recommendations related to continuing, changing, or terminating the trial.

The study leadership will provide information on cumulative toxicities and relevant recommendations to the local principal investigators to be shared with their IRB's.

## **17.0 STATISTICS**

The primary goal will be to determine the response rate of the combination of nivolumab and ablation.

### **17.1 Statistical Methods:**

Let 'p' be the probability of response to treatment

Null hypothesis             $H_0: p = p_0$   
Alternate hypothesis       $H_1: p >= p_1$

This study is a phase II non-randomized clinical trial. The primary endpoint of this trial is to determine the response rate for patients with metastatic non-small cell lung cancer treated with a combination of nivolumab and ablation, in the second line setting. Historically, the response rate of nivolumab alone in this setting has been about 20%.

Simon's minimax two-stage design (Simon, 1989) will be used. The null hypothesis that the true response rate is 20% will be tested against a one-sided alternative. In the first stage, 18 patients will be accrued. If there are 4 or fewer responses in these 18 patients, the study will be stopped early for futility. If at least 5 responses are obtained, additional patients will be accrued for a total of 33. The null hypothesis will be rejected if 11 or more responses are observed in 33 patients. This design yields a type I error rate of 0.05 and power of 80% when the true response rate is 40%.

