**Protocol Rationale:** Nivolumab releases the inhibition of the immune system against human cancers. Dramatic and sustained activity has been observed in advanced lung cancer. Ablation may stimulate the immune system by exposing new tumor antigens. Since tumors that express PD-L1 may be more likely to respond to nivolumab, if ablation increases PD-L1 expression (which has not been studied) this treatment may enhance the activity of nivolumab at both the treated site and in other, non-treated, tumors. Ablation is already an FDA approved treatment for cancer. Nivolumab was recently FDA approved for second line treatment of advanced squamous cell NSCLC. The goal of the study will be to determine if the combination of nivolumab and ablation has higher systemic activity than previously reported with nivolumab alone.

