## **7.0 RESPONSE ASSESSMENT:**

**7.1. Objective Response Rate by RECIST:** Response Evaluation Criteria in Solid Tumors (RECIST), version 1.1 will be used to assess responses by CT/ MRI but response criteria are modified by the immune-related response criteria as described in section 7.3. The first scheduled assessment of tumor response will be performed approximately 12 weeks after the first dose of nivolumab and approximately every 12 weeks thereafter. Patients in whom a scheduled scan showed initial disease progression will be allowed to continue receiving treatment until a confirmatory scan was obtained at least 1 month later. (see section 7.3)

Use of RECIST to clinically assess response for patients who progress with sum of target lesion is > 20 % then should use IrRC (if patient is asymptomatic, no vital organ involved etc.)

**7.2.** Overall responses derived from investigator reported data, with assessment according to immune-related response criteria.

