#### **7.4 Modified immune-related response criteria (irRC), derived from RECIST 1.1**

This new classification is based on the recent learning from clinical studies with cancer immunotherapies that even if some new lesions appear at the beginning of a treatment or if the total tumor burden does not increase substantially, tumor regressions or stabilizations might still occur later. The irRC were created using bidimensional measurements (as previously widely used in the World Health Organization criteria). For this trial, the concepts of the irRC are combined with RECIST 1.1 to come up with the modified irRC.

For modified irRC, only target and measurable lesions are taken into account. In contrast to the RECIST 1.1 criteria, the modified irRC criteria (a) require confirmation of both progression and response by imaging at 12 weeks after initial imaging and (b) do not necessarily score the appearance of new lesions as progressive disease if the sum of lesion diameters of target lesions (minimum of 10 mm per lesion, maximum of 5 target lesions, maximum of 2 per organ) and measurable new lesions does not increase by  $\geq 20\%$ .

The same method of assessment and the same technique should be used to characterize each identified and reported target lesion(s) at baseline, during the trial, and at the end of trial visit. All measurements should be recorded in metric notation. The modified irRC based on RECIST 1.1 are displayed below.

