**Overall Responses Derived from Changes in Index, Non-Index, and New Lesions**

Measurable Response	Non-Measurable Response		Overall Response Using Modified irRC
Index and New, Measurable Lesions	Non-Index Lesions	New, Non-Measurable Lesions	
Decrease 100%	Absent	Absent	irCR 
Decrease 100%	Stable	Any	irPR 
Decrease 100%	Unequivocal progression	Any	irPR 
Decrease $\geq 30\%$	Absent / Stable	Any	irPR 
Decrease $\geq 30\%$	Unequivocal progression	Any	irPR 
Decrease $< 30\%$ to increase $< 20\%$	Absent / Stable	Any	irSD
Decrease $< 30\%$ to increase $< 20\%$	Unequivocal progression	Any	irSD
Increase $\geq 20\%$	Any	Any	irPD

 Decreases assessed relative to baseline

 Assuming that the response (irCR and irPR) and progression (irPD) are confirmed by a second, consecutive assessment at least 4 weeks apart (normally it should be done 6 weeks apart).

Post Ablation changes observed on radiographic studies that are larger in size than preablation masses will not be considered tumor progression if no enhancement within the lesion that suggests tumor growth.

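### The two-stage rule tests a response count scored on criteria assembled for this trial against a nivolumab-alone rate of about 20% that is not shown to be on the same criteria, so the 0.05 is assured only if that rate is at most about 20.3% on the scale used

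*Protocol*

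**What the plan says.** The stated aim (Protocol 2.0, Protocol Rationale) is to "determine if the combination of nivolumab and ablation has higher systemic activity than previously reported with nivolumab alone". There is no control arm, so the comparison rests on one benchmark. Section 17.1 says: "Historically, the response rate of nivolumab alone in this setting has been about 20" per cent. It then says: "The null hypothesis that the true response rate is 20% will be tested against a one-sided alternative". The SAP repeats both statements. Neither document cites a report for the 20%, states the criteria behind it, or says which definition of response feeds the test.

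The rule is a Simon minimax design with a first stage of 18. Its stopping rule reads: "If there are 4 or fewer responses in these 18 patients, the study will be stopped early for futility". With 5 or more responses accrual goes on to 33, and the null is rejected at 11 or more. The stated properties are a type I error of 0.05 and 80% power at 40%.

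The numerator is defined in section 7:

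- Section 7.1 starts from RECIST 1.1 but says the criteria are modified by immune-related criteria.
- Section 7.2 says: "Overall responses derived from investigator reported data, with assessment according to immune-related response criteria".
- Section 7.4 says: "For this trial, the concepts of the irRC are combined with RECIST 1.1 to come up with the modified irRC". It contrasts the result with RECIST 1.1.
- The overall-response table in 7.4 gives irPR for a fall of at least 30% in index plus new measurable lesions, even where non-index lesions show "Unequivocal progression" and whatever the status of new non-measurable lesions.
- Section 7.4 also adds new measurable lesions to the tumour burden and requires irCR and irPR to be confirmed.
- A note under the table says that post-ablation enlargement without enhancement suggesting tumour growth is not progression.

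**The concern.** A single-arm test against a historical rate is only as good as the match between the two measurements. Here the count is on criteria assembled for this trial, while the benchmark is an unsourced figure on unstated criteria. Nothing in either document gives a nivolumab-alone rate on the modified irRC or argues that the change of criteria is neutral.

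If nivolumab alone would score a few points above 20% on the modified irRC, a pass could credit ablation with an effect of the criteria. If it would score lower, the rule is harder to pass than planned and a useful regimen could be dropped. No other feature of the design would reveal either error.

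This is separate from the question of how the parts of section 7 fit together. Even if section 7 were settled entirely in favour of the modified irRC, the 20% would still not be shown to belong to it.

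**Working it through.** **Inputs.** From 17.1: n1 = 18, continue at 5 or more, n = 33, reject at 11 or more, p0 = 0.20, p1 = 0.40. The documents give no nivolumab-alone rate on the modified irRC, so the rates tried in steps 2 and 3 are assumptions, shown as a range.

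**Formula.** With true response rate p, the probability of passing is

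P(pass | p) = Σ (x = 5 to 18) P(X1 = x) × P(X2 ≥ 11 − x), where X1 ~ Bin(18, p) and X2 ~ Bin(15, p).

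**Step 1: the plan's own figures.** At p = 0.20:

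| x | P(X1 = x) | P(X2 ≥ 11 − x) | product |
|---|---|---|---|
| 5 | 0.1507 | 0.0611 | 0.0092 |
| 6 | 0.0817 | 0.1642 | 0.0134 |
| 7 | 0.0350 | 0.3518 | 0.0123 |
| 8 | 0.0120 | 0.6020 | 0.0072 |
| 9 | 0.0033 | 0.8329 | 0.0028 |
| 10 or more | | | 0.0009 |

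The sum is 0.0458, within the nominal 0.05. At p = 0.40 the same formula gives 0.8011. An exhaustive search at p0 = 0.20, p1 = 0.40, error ≤ 0.05 and power ≥ 0.80 returns this same minimax design. The stated figures are reproduced.

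**Step 2: the same rule if nivolumab alone has a different rate on the scale counted (assumed), with no benefit from ablation.**

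| assumed rate | P(pass) |
|---|---|
| 15% | 0.006 |
| 17% | 0.015 |
| 19% | 0.033 |
| 20% | 0.046 |
| 21% | 0.062 |
| 22% | 0.082 |
| 23% | 0.106 |
| 24% | 0.134 |
| 25% | 0.166 |

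Solving P(pass | p) = 0.05 gives p = 0.203. The error reaches twice its value at 20% (2 × 0.0458 = 0.0916) at p = 0.224. That is a shift of 2.4 points, less than one patient in 33 (1/33 = 3.0 points).

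**Step 3: power if confirmation lowers the counted rate (assumed).** A regimen with a true 40% on the benchmark's scale that is counted at 38% passes with probability 0.733. Counted at 35%, it passes with probability 0.609.

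**Step 4: direction.** These features of 7.4 can raise the count relative to RECIST 1.1:

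- irPR is allowed despite unequivocal non-index progression.
- irPR is allowed with any new non-measurable lesions.

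These can lower it or limit the increase:

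- New measurable lesions are added to the sum, so the 30% fall must be net of them.
- irCR and irPR need confirmation, which lowers the count if the benchmark did not require it.

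The documents hold no data with which to weigh one set against the other.

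**The case against.** The strongest reply is that the rule does what it says: 0.0458 at 20% and 0.8011 at 40%. That stands. A reader might infer that the rule fails to hold its 0.05. The documents do not support this, because any excess depends on an upward shift that they neither report nor imply. Under a downward shift, 0.05 remains a valid upper bound.

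Second, a reader might infer that the modified irRC is simply looser and accepts patients with new lesions as responders. That is too broad. Only new non-measurable lesions and non-index progression are tolerated outright, and confirmation works the other way.

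Third, the background rates leave some room: 15% partial response in the expanded phase I study, 13/74 = 17.6% from its histology subgroups (6/18 and 7/56), and 19% in the randomized non-squamous trial. Starting from 19%, about 1.3 points of upward shift fit below 20.3%; from 17.6%, about 2.7 points. This stands as a reason not to presume inflation. It does not close the gap, because those rates are also given without criteria and 17.1 does not say that the 20% was rounded up to allow for them.

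Fourth, section 7.3 governs treatment beyond progression. It does not say that shrinkage after an initial RECIST 1.1 progression enters the primary count. A reader might infer that from 7.2 and 7.4, but it is not written.

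Finally, the shifts in steps 2 and 3 would look the same for a difference in case mix. They show how sensitive the rule is and are not evidence of a criteria effect.

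**Conclusion.** The point holds in conditional form. The benchmark and the count are not shown to be on one scale. The design's arithmetic is correct, but its 0.05 carries over to the intended comparison only if nivolumab alone yields at most about 20.3% on the scale used, and neither document shows this. The margin above 20% is 0.3 points.

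The size of any error rests wholly on an assumed rate, and its direction cannot be settled from the documents. Because the direction is open, both outcomes are hard to read: a pass might reflect the criteria, and a failure might reflect the confirmation requirement. The matter should be corrected before the counts are used, but it does not invalidate the design.

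**What to change.** In 17.1 and the SAP:

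1. Name the report behind the 20%, with its response and confirmation criteria.
2. State that responses at 5/18 and 11/33 are counted on those same criteria. Unless the source used others, that means best overall response of CR or PR by RECIST 1.1, reached before RECIST 1.1 progression.
3. Keep the 7.4 note on non-enhancing post-ablation enlargement in that count. Without it, an enlarging ablation zone could be scored as progression and wrongly disqualify a responder.
4. Report the modified irRC response rate as a secondary result, not tested against 20%.

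The treatment decisions in 7.3 need no change for this purpose.

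The cost is wording in two documents and a second classification of measurements already collected, with no new patients or scans. The downside is that responses seen only under the modified irRC no longer count toward go/no-go.

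Keeping the modified irRC as the primary scale would also be coherent, but it needs a justified null on that scale, which the documents do not supply, and it may cost power. With 18/33 and the stage 1 rule unchanged, an assumed null of 22% needs 12/33 (error 0.041, power at 40% 0.709), and 25% needs 13/33 (error 0.047, power 0.587).
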